16.7 Missing Data and Dropouts

In the primary analysis, missing and drop-out urine drug testing data will be imputed as MA use. On trial completion we will consider sensitivity analyses to investigate the extent to which the results of the main analysis of the primary outcome depend on the assumptions made about missing values. An extremely simple approach imputes missing as non-use and re-analyzes the outcome. If the conclusions are the same, there is little else necessary to do, but this is unlikely. Multiple imputation (MI) is one way to explore more complex possibilities. In MI, non-missing data are used to impute missing data under a missing-at-random (MAR) assumption. MAR seems an

unlikely hypothesis in a substance use trial, but the missing-not-at-random (MNAR) hypotheses may be introduced to explore sensitivity as detailed below.

To explore MNAR alternatives, we shift the values of the imputations by a chosen shift value. We choose the shift value for the two arms of the trial separately. A p-value for the primary outcome can then be calculated for every shift pair via multiple imputation. The pair can be plotted on two axes: one axis for the control shift, and one for the treated shift. This generates a p-value surface showing regions in which the trial is significant or not as a function of the MNAR assumptions. The primary outcome is a single point on this surface. If the primary outcome is surrounded by a large region of MNAR assumptions that agree with the primary concerning the significance of the outcome, this will lend credence to the primary outcome. But if the primary outcome is close to points that disagree, this will cast doubt on the primary analysis' conclusion.

Sensitivity analyses will be done for secondary analyses where appropriate to determine the possible effects of missing data on the final results.

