11.4.2 Timeline Followback (TLFB)

The Timeline Followback procedure⁵⁰ will be used to elicit the participant's self-reported use of substances, including MA, opioids, and MA/opioid co-use during the screening phase and throughout study participation. During the screening phase, this form will be used to assess substance use for the 30-day period prior to written consent. During the trial, TLFB will be administered to document the participant's self-reported use of substances for each day since the previous TLFB assessment. For participants who report opioid use or who have a positive urine drug screen for opioids during the trial, Medical Clinicians will offer them the opportunity to withdraw from the medication aspects of the trial and to initiate MOUD through a referral to appropriate care. In the event that participants decline this offer, this will be recorded in the participant's study record.

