16.2 Rationale for Sample Size and Statistical Power

A sample size of 246 was chosen for this study to provide 90% power to detect a statistically significant difference between the two treatments. Power was based on an effect size derived from the proportion of MA-negative urines during the last 4 weeks of Phase I of the ADAPT-2 study (CTN-0068) comparing the active treatment arm to the placebo arm. Imputing all missing data as positive, the relevant proportions in ADAPT-2 were 0.17 and 0.07 in the treated (AMC) and control (PBO) arms respectively, so we take the treatment effect of interest for MURB to be a risk difference of 0.10 corresponding to an odds ratio of 2.72. This outcome from the ADAPT-2 study was chosen because it was believed to be the most comparable available result using this substance-using population to the BUP-Inj outcome for this study.

To simulate data for CTN-0110, we first imputed all missing ADAPT-2 visits as UDS-positive for MA, then bootstrapped the ADAPT-2 participants, keeping the participant's site and visits together, thus respecting whatever temporal and site-dependent correlations might exist in the data. We assumed equal treatment allocation. To draw bootstrap samples of size N, we bootstrapped differently under null and alternative hypotheses as follows:

- Null: We treated the two simulated treatments the same way: for each of the N/2 simulated participants receiving that treatment, we flipped a fair coin to decide which ADAPT-2 arm (109 AMC and 294 PBO) to draw it from, and then drew it randomly with replacement from that arm.

- Alternative: For AMC, we drew $N/2$ observations randomly with replacement from the 109 AMC patients. For PBO, we drew $N/2$ observations randomly with replacement from the 294 PBO patients.

[figure not shown]
To simulate 2 UDS per week we used all 8 visits of a participant in order. The model under which we performed the power analysis is the same as that to be used for the primary analysis, discussed in Section 16.3.

Simulated power for the generalized estimating equation⁶⁹ is shown as a function of total N ($N/2$ in each arm) in Table 16.1 and in Figure 16.1, in which the total sample size required for power (0.8, 0.9) is interpolated from the simulated data using a logistic function, and estimated to be (182, 246).

Table 16.1: Simulated power for the GEE as a function of total N ($N/2$ in each arm)

Total N	Power
100	0.55
150	0.74
200	0.84
250	0.91
300	0.96
350	0.97

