16.3 Statistical Methods for Primary and Secondary Outcomes

16.3.1 Primary Outcome

UDS will be collected twice a week during Weeks 9 through 12, or 8 assessments. For each assessment, the outcome will be 1 if the UDS is MA negative and 0 if the UDS is MA positive or missing. The probability of an MA negative UDS during Weeks 9-12 will be computed via a GEE approach postulating a binomial distribution with a logit link, an AR(1) correlation for the repeated observations of a single participant, and utilizing the robust (sandwich) estimator for the covariance of the regression betas. Despite other possible sources of variance such as random site effects, the regression coefficients will be asymptotically unbiased with consistent standard errors using this estimation strategy. The model will have a term for treatment group (BUP-Inj and PBO-Inj) as the between-subjects factor. The model will be used to compute an average probability of MA-negative UDS across Weeks 9 through 12 in each group. Letting y_{it} be an indicator of whether the UDS for participant i ($i=1, \dots, n$) at timepoint t during this evaluation period ($t=1, \dots, 8$), and z_i is an indicator of participant i being assigned to the BUP-Inj arm, the logistic model is given by

$$\text{logit } P(y_{it} = 1) = \alpha + \beta z_i.$$

The hypothesis will be tested by the statistical significance of the odds ratio using a two-sided test (i.e., $H_0: e^\beta = 1$; $H_1: e^\beta \neq 1$). An *a priori* alpha (i.e., type I error) of 0.05 will be used for this analysis.

SAS code to estimate the primary outcome follows:

```
proc genmod data = dat;
  class patid treat;
  model metneg(event = "1") = treat / dist = bin link = logit;
  repeated subject = patid / type = ar(1);
  run;
```

Where `patid` is the participant's unique identifier, `treat` is an indicator of being assigned to the BUP-Inj treatment arm, and `metneg` is an indicator of whether the UDS is negative for MA.

16.3.2 Secondary Outcomes (medication phase, Weeks 1-12):

1. *Alternate measures of methamphetamine use: both*

- a. MA Treatment Effectiveness Score (TES), as measured by number of UDS results negative for MA by condition, during Weeks 1-12 (score range 0-24) will be analyzed as count data, which typically follows a Poisson distribution.

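### Section 16.7 treats agreement between 'all missing = use' and 'all missing = non-use' as enough, but two analyses that handle both arms alike do not bound the result if missing samples differ by arm

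*Combined protocol and SAP*

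**What the plan says.** Section 16.3.1 fixes the primary coding: "the outcome will be 1 if the UDS is MA negative and 0 if the UDS is MA positive or missing". The planning rates in Section 16.2 were built the same way: "Imputing all missing data as positive, the relevant proportions in ADAPT-2 were 0.17 and 0.07".

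Section 16.7 opens its sensitivity plan conditionally: "On trial completion we will consider sensitivity analyses to investigate the extent to which the results of the main analysis" depend on the missing-data assumptions. The first check is "An extremely simple approach imputes missing as non-use and re-analyzes the outcome", followed directly by "If the conclusions are the same, there is little else necessary to do, but this is unlikely".

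The section then turns to multiple imputation and says that "the missing-not-at-random (MNAR) hypotheses may be introduced to explore sensitivity". The method is a p-value surface over pairs of shifts: "We choose the shift value for the two arms of the trial separately". It adds that a primary result lying close to disagreeing points on the surface would be in doubt. No missing rate or pattern is given.

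**The concern.** The two simple analyses are two corners of the section's own surface: all missing samples positive in both arms, and all negative in both arms. The extremes of the treatment effect lie at the other two corners, where the arms are treated in opposite ways. Agreement at the first pair does not control what happens at the second.

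If the sentence is followed, a result that rests on the missing-equals-use assumption can be called robust without the one analysis that tests arm-specific departures. The choice would also be made after the data are seen.

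Arm-differential missingness is conceivable here. Section 11.4.2 provides for participants found to be using opioids after enrolment: "Medical Clinicians will offer them the opportunity to withdraw from the medication aspects of the trial and to initiate MOUD through a referral". If that route, or any other route to missed visits, is used differently by arm, the missing samples need not behave alike.

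**Working it through.** **1. The plan's own figures.** The odds ratio is (0.17/0.83)/(0.07/0.93) = 2.72, as Section 16.2 states. N = 246 gives 123 per arm. The plan's bootstrap cannot be rerun without the earlier trial's participant data, so I express the stated power as a variance factor f, where the variance of a participant's mean over the 8 samples is f·p(1-p).

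- ln(OR) = 1.0011. For 90% power at two-sided 0.05, SE = 1.0011/3.2415 = 0.3088, so SE² = 0.0954.
- With f = 1, SE² = 1/(123×0.17×0.83) + 1/(123×0.07×0.93) = 0.0576 + 0.1249 = 0.1825.
- Hence f = 0.0954/0.1825 = 0.523. The six rows of Table 16.1 give 0.49 to 0.53.
- A conservative alternative is 123/220 = 0.559, because the simple two-proportion formula needs 220 per arm.

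Ranges below span f = 0.523 to 0.559.

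**2. The algebra.** Let m1 and m0 be the missing rates (BUP-Inj, placebo), q1 and q0 the MA-negative shares among missing samples, and d the difference with all missing positive. Then

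risk difference = d + q1·m1 - q0·m0.

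The simple analyses test only (q1, q0) = (0,0) and (1,1). The possible range is d - m0 to d + m1. At 20% missing in both arms, both simple analyses give 0.10, and the range is 0.10 - 0.20 = -0.10 to 0.10 + 0.20 = +0.30.

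**3. Do the two analyses agree at the design rates?** I use a Wald test on the log odds ratio, with SE² summed over arms of v/(123·(p(1-p))²). Missing = use gives p = 0.001-0.002. Missing = non-use compares 0.17+m with 0.07+m under two patterns:

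- Constant f (roughly intermittent missingness): v = f·p'(1-p') at the new rates p'. At 20%: ln(OR) for 0.37 vs 0.27 is 0.462, SE² = 0.523×(0.0349 + 0.0412) = 0.0398, z = 2.32, p = 0.020.
- Whole-participant dropout: v = f·p(1-p) + m(1-m) - 2pm. At 20%: v = 0.1658 and 0.1660, SE² = 0.0248 + 0.0348 = 0.0596, z = 1.89, p = 0.058.

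**4. Tipping share.** Count missing BUP-Inj samples as use and test 0.17 against 0.07 + q·m0. At m0 = 0.20 with f = 0.523, q = 0.185 gives a placebo rate of 0.107, ln(OR) 0.536, SE² = 0.523×(0.0576 + 0.0851) = 0.0746 and z = 1.96. For dropout, replace m by q·m0 in the dropout variance.

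| Missing per arm | Non-use p, constant f | Non-use p, dropout | Tipping share, constant f | Tipping share, dropout | Observed placebo rate, 0.07/(1-m) |
|---|---|---|---|---|---|
| 5% | 0.004-0.006 | 0.012-0.013 | 70-74% | 62-65% | 7.4% |
| 10% | 0.009-0.012 | 0.028-0.030 | 35-37% | 31-33% | 7.8% |
| 20% | 0.020-0.025 | 0.058-0.061 | 18-19% | 16% | 8.8% |
| 30% | 0.028-0.034 | 0.076-0.079 | 12% | 10-11% | 10.0% |
| 40% | 0.030-0.036 | 0.080-0.083 | 9% | 8% | 11.7% |

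The simple analyses agree throughout under constant f. Under dropout they agree at 5-10% but not from about 20%.

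**5. Unequal missing rates.** At 30% BUP-Inj and 20% placebo missing, non-use compares 0.47 with 0.27: the difference doubles to 0.20 (p < 0.001 under both patterns), so agreement looks stronger. The tipping share depends only on the placebo rate and stays at 16-19%. At 20% and 30% the other way round, non-use gives 0.37 vs 0.37, and the simple check does raise the alarm.

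**6. Simulation.** Trials had 8 beta-binomial samples per participant, equal missing rates by arm and a participant-level robust Wald test in place of the AR(1) GEE. At 20% missing, among trials with a significant primary result, the non-use analysis was also significant in about 91% (intermittent) or about half (dropout). Among those agreeing trials, with missing BUP-Inj samples as use, significance was lost in 37-44% if 20% of missing placebo samples were negative, and in 12-17% if 10% were.

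Agreement on a null result is no safer. In a separate simulation with 0.12 in both arms, whole-participant dropout and 10-30% missing, both simple analyses were non-significant in about 90% of trials. In 98-100% of those, at least one opposite-direction corner was significant.

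**The case against.** The strongest reply is that the remedy is already in the section. The surface covers every pair of arm-specific shifts, the plan expects the simple analyses to disagree, and the sentence says little else, not nothing else. Section 16.0 also defers detail to a formal SAP still to be written, which might make the surface mandatory. All of this lowers the weight of the point. It does not repair the stated rule: the surface is only conditional, and it is waived in exactly the case where agreement would mislead.

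Second, the mechanism is conjecture. The offer in Section 11.4.2 is to leave the medication aspects only, and Section 10.10 has staff encourage such participants to keep attending twice-weekly visits. Nothing in the documents shows that missingness will differ by arm. That stands, but neither do they show that the arms will behave alike.

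Third, counting every missing BUP-Inj sample as use is the least favourable case. That also stands. If missing placebo samples are negative only at the observed placebo rate, significance at the design values holds to about 31-35% missing, and at 20% missing only about 8-14% of agreeing simulated trials lose it.

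Finally, with whole-participant dropout from about 20% missing, the simple analyses disagree at the design rates, so the shortcut would not apply. This narrows the window for harm to intermittent missingness or chance agreement, but does not close it.

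**Conclusion.** The concern holds. Agreement of the two arm-symmetric analyses does not establish robustness, and the sentence that says it nearly does is wrong as written. That conclusion is algebraic and needs no assumed missing rate.

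Its practical size does depend on assumptions: the missing rate and pattern, the design rates being realised, f between 0.523 and 0.559, and missing BUP-Inj samples counted as use. On these, the concern is small at 5-10% missing, where at least 31% of missing placebo samples would have to be negative to overturn the result. It becomes material from about 20%, where 16-19% would suffice. The opposite-direction corners are bounds, not likely scenarios; the tipping share is the more useful summary. The defect is the shortcut, since the section does contain a suitable method.

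**What to change.** In Section 16.7, delete the sentence about agreement making further work largely unnecessary. State that the arm-specific shift surface will be run whatever the two simple analyses show, that it will include opposite-direction shift pairs, and that the report will say where on the surface significance is lost. Carry the same commitment into the standalone SAP.

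The cost is a wording change and a little more analysis, since the surface is already described. The robustness statement may come out less favourable. The primary test, alpha and sample size are unaffected.

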16.8 Demographic and Baseline Characteristics

Baseline demographic and clinical variables will be summarized for participants enrolled in the active medication phase of the trial. Descriptive summaries of the distribution of continuous baseline variables will be presented with percentiles (median, 25th and 75th percentiles), and with mean and standard deviation. Categorical variables will be summarized in terms of frequencies and percentages.

16.8.1 Subgroup Analyses

Per NIH policy, subgroup analyses will be implemented to assess whether sex, race and/or ethnicity are effect modifiers. For each demographic, a model will be fit including an interaction with treatment assignment and the subgroup effect will be reflected by a two-sided test of whether the interaction regression coefficient is different from zero. Additionally, the treatment effect will be presented for each category of the demographic factor from these interaction models.

16.9 Safety Analysis

Treatment emergent adverse events (AEs), including treatment emergent serious adverse events (SAEs), will be summarized by presenting the number of events, number of participants experiencing AEs, and the severity and relatedness of adverse events by treatment arm. All adverse events will be coded using MedDRA® (The Medical Dictionary for Regulatory Activities). The number and proportion of participants experiencing each treatment emergent AE will be provided overall and by treatment arm. Treatment emergent adverse events will be summarized by System Organ Class (SOC) and Preferred Term (PT). If a participant experiences multiple episodes of an event, then the event is only counted once. Detailed listings of treatment emergent adverse events and non-treatment emergent events in the safety population by treatment arm will be provided and include severity, relationship to study medication(s), and action taken, as available. The criteria for an immediate study review by the DSMB will be monitored closely. These criteria are either (1) three or more participants experience severe adverse reactions; (2) four or more participants have four consecutive positive urine toxicology screens for opioid use,

and have been reevaluated through any means as having moderate to severe opioid use disorder; or (3) one or more SUSAR.

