There are serious risks for overdose and death should BUP-Inj be injected intravenously. A chain of custody will be maintained and documented detailing transfer from the manufacturer to the study pharmacy to the site staff who will administer the BUP-Inj product to participants assigned to the BUP-Inj condition, under the oversight of the Medical Clinicians with DEA Registrations. No take home injectable medications will be provided – all study products will be prepared and administered to study participants at the research clinic. To document safety and drug accountability, the Risk Evaluation and Mitigation Strategy (REMS) procedures will be followed.

There are expected adverse events to the BUP-Inj medication. Medication-related adverse events that occur in more than 5% of subjects when using BUP-Inj include constipation, headache, nausea, injection site pruritus, vomiting, increased hepatic enzymes, fatigue, and injection site pain. These are minor, will be treated with ancillary medications, and tolerable in comparison to protection from overdose and potential for treating MUD⁴². BUP-Inj medication is habit forming. The risks to PBO-Inj are mild, including injection site reactions and tolerable withdrawal symptoms. To avoid risks for iatrogenic illness, all participants must meet criteria for moderate to severe MUD and mild OUD or demonstrate opioid misuse. Throughout the study, management of complaints of opioid withdrawal symptoms for all participants will include provision of over-the-counter medications for head and body aches (e.g., ibuprofen), insomnia (e.g., diphenhydramine), diarrhea (e.g., loperamide) and stomach upset (e.g., bismuth subsalicylate) and ongoing opioid

use will be monitored to ensure that any escalation of opioid use that suggests moderate or greater OUD is evaluated by the Medical Clinician.

Participants assigned to the active condition may acquire opioid dependence by the end of the trial, though concern is mitigated somewhat by the requirement for participants to have mild OUD or opioid misuse. To enroll, individuals must be experienced in the use of opioids, perhaps even including buprenorphine. This risk is balanced by several factors:

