8.2 Participant Exclusion Criteria

Individuals meeting any of the exclusion criteria will be excluded from being randomized into the study.

Study participants **must not**:

1. Have suicidal or homicidal ideation that requires immediate attention;
2. Have evidence of prolongation of the QTc or any other finding on the screening ECG that, in the opinion of the Medical Clinician, would preclude safe participation in the study (e.g., hypokalemia, unstable atrial fibrillation) and be at significant risk for serious cardiac adverse events;
3. Have a laboratory value with total bilirubin $\geq 1.5 \times$ upper limit of normal (ULN), alanine aminotransferase (ALT) $\geq 3 \times$ ULN, aspartate aminotransferase (AST) $\geq 5 \times$ ULN, or serum creatinine $>2 \times$ ULN;
4. Have been in a study of pharmacological or behavioral treatment for addiction within 6 months prior to written study consent (smoking cessation excepted);
5. Have taken an investigational drug in another study within 30 days prior to written study consent;
6. Have been prescribed or have taken buprenorphine or methadone within 30 days prior to written study consent;
7. Be concurrently enrolled in formal behavioral or pharmacological addiction treatment services or express the desire to initiate MOUD at the time of written consent;
8. Be receiving ongoing treatment of medications that are clinically relevant CYP 3A4 or CYP 2C8 inducers or inhibitors (e.g., rifampicin, azole antifungals, macrolide antibiotics), Class IA antiarrhythmic medications (e.g., quinidine, procainamide, disopyramide) or Class III antiarrhythmic medications (e.g., sotalol, amiodarone) at the time of randomization that, in the judgment of the Medical Clinician, could interact adversely with study medications or put them at significant risk for development of serotonin syndrome;
9. Have a current pattern of alcohol, benzodiazepine, or other sedative hypnotic use which would preclude safe participation in the study as determined by the Medical Clinician;
10. Have a surgery planned or scheduled, or other treatment that would require the use of opioid-containing medications (e.g., opioid analgesics) during the study period;
11. Currently or soon to be in jail or prison; currently in any inpatient overnight facility as required by court of law or have pending legal action or other situation that could prevent participation in the study or in any study activities;

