Cognitive Behavioral Therapy Documentation			X	X	X	X	X	X	X	X	X	X	X	X	X	X
Iowa Gambling Task and Documentation		X*														
Treatment Effectiveness Assessment																X ²
Cannabis Use Assessment			X													
Tobacco Use History (PhenX Tier 1)			X													X ²
Quality of Life (PhenX Tier 1)			X													X ²
Semi-Structured Qualitative Interview			X ^E													
Adherence Measures																
Buprenorphine-XR/Placebo Injection				X ²				X				X				
BUP-SL Dispensing				X ¹												
Laboratory Evaluations																
Urine Screening for Disease			X*												X	
Complete Blood Count			X*												X	
Blood Chemistry			X*													
Liver Function Tests			X*												X	
Disease Serology			X*												X	
Blood Sample for UTSW Repository			X*												X	
Blood Sample for NIDA Genetic Testing and Family Origin								X ^C								

Study Phase	Prescreening	Screening	Medication Phase												Follow-up
			1	2	3	4	5	6	7	8	9	10	11	12	
Study Week		-21 to -1	1	2	3	4	5	6	7	8	9	10	11	12	16
Buprenorphine Blood Levels							X ^A				X ^A			X	
Administrative and Other Forms															
Locator Form		X*			X		X			X			X		
Eligibility - Randomization (Enrollment Form)			X												
Visit Documentation Form		X+	2X	2X	2X	2X	2X	2X	2X	2X	2X	2X	2X	2X	X
Mental Health Follow-Up Assessment ^B															
End of Medication Form														X ²	
Protocol Deviation and Review ^B															
Treatment Satisfaction															X
Study Completion															X

NOTES:

X* = once during screening

X+ = at each screening visit

X^A = at each induction visit, including if additional induction visits are required during the medication phase, and on the day of first injection

X = a procedure or assessment performed once per week and preferably at the first visit of the week, unless otherwise noted

2X = a procedure or assessment performed twice per week

X¹ = on the day of induction only

X² = collected at the second visit of the week

^A Must be collected prior to administration of any medications at the visit

^B Completed as applicable

^C If consent is provided, collect sample on day of 2nd injection if possible. Otherwise, to be collected at any future visit with blood draw.

^D Collected at screening visit(s) with a UDS negative for opioids and on the day of expected randomization

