11.3.2 Electrocardiogram (ECG)

A 12-lead ECG will be administered to assist in determination of participant eligibility and again to assess safety. The ECG tracings will be reviewed by a Medical Clinician for accuracy and transmitted to be read by a central cardiologist. Results from the central cardiologist's interpretation will be assessed by a Medical Clinician.

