11.6.2 Complete Blood Count, Blood Chemistry, and Liver Function Tests

Complete blood counts (CBC), blood chemistry (BUN and creatinine), and liver function tests (AST, ALT, ALP, and bilirubin) will be performed to help determine eligibility at screening. A CBC and LFTs will be repeated for safety monitoring in the final week of the medication phase. An accredited local laboratory (College of American Pathologists or equivalent) that meets CLIA guidelines will perform testing, provide normal values, and provide proof of lab certifications.

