17.17.5 Known Potential Toxicities of Study Medication

Specific known potential toxicities of the study medication include risk of overdose. Buprenorphine, as Sublocade™ in this study, is a Schedule III controlled substance. An IND will be on file with the FDA to provide safety monitoring. The medication will be handled and administered using the required REMS procedures. All other clinical considerations regarding risk for use of this medication, such as possible drug interactions or hepatic impairment, have been integrated in the exclusion criteria and safety monitoring procedures utilized in this study.

Refer to the package insert for Sublocade™ for complete list of adverse reactions and toxicities.

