23.0 APPENDIX A: ADVERSE EVENT REPORTING AND PROCEDURES

Each participating site's Principal Investigator is responsible for study oversight, including ensuring human research subject protection by designating appropriately qualified and trained study personnel to assess, report, and monitor adverse events.

Definition of Adverse Events and Serious Adverse Events

An **adverse event** (AE) is any untoward medical occurrence in humans, whether or not considered study medication related which occurs during the conduct of a clinical trial. Any change from baseline in clinical status, ECGs, lab results, x-rays, physical examinations, etc., that is considered clinically significant by the Medical Clinician are considered AEs.

Suspected adverse reaction is any adverse event for which there is a reasonable possibility that the study medication/intervention caused the adverse event. A reasonable possibility implies that there is evidence that the study medication caused the event.

Adverse reaction is any adverse event caused by the study medication.

An **adverse event, suspected adverse reaction, or adverse reaction** is considered “**serious**” (i.e., a serious adverse event, serious suspected adverse reaction or serious adverse reaction) if, in the view of either the Medical Clinician or Sponsor, it:

- 1) Results in death: A death occurring during the study or which comes to the attention of the study staff during the protocol-defined follow-up period, whether or not considered caused by the study medication(s), must be reported.
- 2) Is life-threatening: Life-threatening means that the study participant was, in the opinion of the Medical Clinician or Sponsor, at immediate risk of death from the reaction as it occurred and required immediate intervention.
- 3) Requires inpatient hospitalization or prolongation of existing hospitalization.
- 4) Results in persistent or significant incapacity or substantial disruption of the ability to conduct normal life functions.
- 5) Is a congenital abnormality or birth defect.
- 6) Is an important medical event that may not result in one of the above outcomes, but may jeopardize the health of the study participant or require medical or surgical intervention to prevent one of the outcomes listed in the above definition of serious event.

Definition of Expectedness

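### Section 16 plans no by-arm analysis of the repeat liver tests or ECG, so enzyme rises are compared between arms only where a clinician calls them clinically significant

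*Combined protocol and SAP*

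**What the plan says.** Measurement. Section 11.6.2 states: "A CBC and LFTs will be repeated for safety monitoring in the final week of the medication phase". Section 11.3.2 states: "A 12-lead ECG will be administered to assist in determination of participant eligibility and again to assess safety"; the tracing goes to a central cardiologist. That section gives no week for the repeat ECG. The Table of Assessments (11.1) gives it the code for "collected at the second visit of the week", which fits Week 12, but the table is broken in the text available.

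Reason for measuring. Section 4.3 lists effects seen in more than 5% of subjects given the drug, ending with "increased hepatic enzymes, fatigue, and injection site pain". Section 17.17.5 says that considerations "such as possible drug interactions or hepatic impairment, have been integrated in the exclusion criteria and safety monitoring procedures". QTc appears as an exclusion criterion in section 8.2: "Have evidence of prolongation of the QTc or any other finding on the screening ECG".

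Analysis. Section 16.9 begins: "Treatment emergent adverse events (AEs), including treatment emergent serious adverse events (SAEs), will be summarized by presenting the number of events". It goes on to participant counts, severity, relatedness, tables by System Organ Class and Preferred Term, and listings. Section 16.6 item 8 plans Chi-square tests on adverse events and overdoses.

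The link between the two. Appendix A counts as adverse events "Any change from baseline in clinical status, ECGs, lab results, x-rays, physical examinations, etc., that is considered clinically significant by the Medical Clinician".

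**The concern.** Numeric values are to be measured in both arms, before and after treatment, for an effect that the protocol itself expects. As section 16 stands, the arm comparison uses only those changes that passed a clinical judgment. No numeric criterion standardises that judgment across the 4 to 8 sites.

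Entry rules make the judgment harder. Section 8.2 admits people with ALT below 3x and AST below 5x the upper limit of normal (ULN). A clinician looking at one patient with a raised screening value may reasonably see a moderate rise as that patient's usual state. A randomised comparison of change from screening does not need that call.

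At stake is a sensitive by-arm description of hepatic effect in what section 4.2.3 calls a novel use of the drug. The last injection is in Week 9 and the only scheduled repeat liver test comes after it. Beyond following up the individual patient, the main use of that test is to compare the arms, and section 16 does not plan this.

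**Working it through.** **Text check.** The documents state no figure on this point, so there is none to reproduce. Setting measurement beside planned use:

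| Item | Measured after screening | By-arm analysis of values in section 16 |
|---|---|---|
| ALT, AST, ALP, bilirubin | Final medication week (11.6.2) | None |
| Blood count, including platelets | Final medication week (11.6.2) | None |
| 12-lead ECG, central reading | Once; Week 12 inferred from 11.1 | None |
| Adverse events, overdoses | Every visit | 16.9 and 16.6 item 8 |

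Sections 7.3, 11.3, 11.6, 16.3 to 16.9, 17.17 and Appendices A and B contain no change-from-screening summary, shift table or threshold count for these values. Section 10.10 gives numeric limits (AST/ALT above 5x ULN, bilirubin above 2x ULN, platelets below 75 x 10^3/uL), but as examples for withdrawing study medication. No analysis counts them. By contrast, 16.6 specifies models for craving, stress, pain, quality of life and Week 12 chlamydia or gonorrhoea.

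**Illustration of size.** The true rates, capture fractions, SDs and 80% availability below are assumptions; none comes from the documents.

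- Participants with Week 12 values: 0.80 x 123 = 98.4, taken as 98 per arm.
- Expected reported cases per arm = n x p x s, where p is the true rate of an elevation and s the share reported as an adverse event.
- Power is for a two-sided Fisher exact test at 0.05, by full enumeration.

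| True rates | s | Expected cases | Power |
|---|---|---|---|
| 10% vs 2% | 1 | 9.8 vs 2.0 | 57% |
| 10% vs 2% | 0.5 | 4.9 vs 1.0 | 19% |
| 10% vs 2% | 0.3 | 2.9 vs 0.6 | 4% |
| 15% vs 3% | 1 | 14.7 vs 2.9 | 81% |
| 15% vs 3% | 0.5 | 7.4 vs 1.5 | 39% |
| 15% vs 3% | 0.3 | 4.4 vs 0.9 | 14% |

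With all 123 per arm and a normal approximation, 10% vs 2% gives 76%, falling to 45% at half capture: the same direction.

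The analyses would be descriptive, so interval width matters more than power. At 10% vs 2% and 98 per arm, the risk difference is 8.0 points with a 95% half-width of 1.96 x sqrt((0.10 x 0.90 + 0.02 x 0.98)/98) = 6.6 points. At half capture it is 4.0 points with a half-width of 1.96 x sqrt((0.05 x 0.95 + 0.01 x 0.99)/98) = 4.7 points. Incomplete capture halves the estimate, and the interval then includes zero.

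For a 20% arm difference in mean ALT on the log scale, z = ln(1.2)/(SD x sqrt(2/98)) = 0.1823/(SD x 0.1429). SDs of 0.4, 0.5 and 0.6 give z = 3.19, 2.55 and 2.13, and power of 89%, 72% and 57%.

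**The case against.** - **The standalone SAP.** Section 16.0 says that a formal SAP will be written and that section 16 gives the general strategies. A reader might infer that the trial will never analyse these values. The documents do not support that: the SAP could specify the tables, and it is not available. This objection stands and limits the point to section 16.
- **QTc.** A reader might infer that QTc prolongation is a named drug risk on a par with the liver. It is not. It is an exclusion criterion in 8.2, and it appears neither in the expected effects in 4.3 nor in 17.17.5. The antiarrhythmic exclusion is worded around adverse interaction, not QTc. What remains is that the ECG is repeated expressly for safety and no summary of it is planned.
- **The capture fractions.** A reader might infer from the table that most hepatic signals would be missed. At ALT of 3x ULN this is weak: everyone at or above 3x is excluded at entry, so any such case is new since screening and crosses a limit that the protocol prints. Clinicians are least likely to pass over those. No passage supports capture of 30% to 50%, and the figure of more than 5% in 4.3 is for raised enzymes as an adverse event, not for 3x ULN. The table shows only that lower capture means less information. The argument is stronger for rises that stay below the entry limits.
- **Availability of the data.** Section 11.3.2 refers to the cardiologist's interpretation and does not say that numeric QTc is recorded. Section 18.5 allows some source data to stay outside the database. Local laboratories set their own normal values (11.6.2), so raw enzyme values should not be pooled. All of this stands and shapes the fix.
- **Priority.** Section 4.3 calls the overall risk low, and the safety-related exploratory objective is adverse events and overdoses. That argues for a descriptive analysis, not against having one.

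**Conclusion.** The point holds within section 16. Followed as written, that section compares a listed drug effect between arms only through a clinical judgment that may vary by site, although the values are to be measured in both arms. This is more than missing detail, because a specific and more sensitive analysis is available at little cost.

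Its size cannot be derived from the documents. Under the assumptions above, reporting half of the elevations halves the visible risk difference (8 to 4 points at 10% vs 2%) and cuts power from 57% to 19%. These figures illustrate the mechanism and do not predict the result. The conclusion itself rests on the text alone. It assumes that the standalone SAP does not already contain these tables; if it does, section 16.9 needs only a reference to it.

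The primary analysis is not affected. The sponsor should make this change before the SAP is final.

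**What to change.** Add to 16.9, or to the SAP with a reference from 16.9, and label as descriptive:

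1. **Population.** Define the safety population, a term that 16.9 uses without a definition, and use it throughout.
2. **Liver values.** Summarise Week 12 ALT, AST and bilirubin by arm as multiples of the local laboratory's ULN, with change from screening. For ALT and AST, fit an ANCOVA of log(value/ULN) on arm, with the screening log(value/ULN) as covariate.
3. **Shift tables.** From screening to Week 12, at limits already printed in 8.2 and 10.10: ALT 3x, AST/ALT 5x, bilirubin 1.5x and 2x ULN, platelets 75 x 10^3/uL. Give risk differences with 95% confidence intervals.
4. **Missing values.** Report the number without Week 12 values by arm. Count unscheduled values that led to withdrawal from study medication in the threshold tables, so that these participants do not drop out of the comparison.
5. **ECG.** Summarise the repeat ECG by arm: QTc change from screening if the central reading records a number, otherwise the categorical interpretation.
6. **Data capture.** Confirm that numeric laboratory results, local ULNs and ECG results enter the database.

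The cost is a few paragraphs and tables, the check on data capture, and a few more descriptive safety comparisons. No dose, schedule or clinical rule changes.
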